### **8.7 Safety Analyses**

Safety will be assessed and relevant parameters will include AEs, serious adverse events (SAEs), laboratory safety tests including hematology (complete blood count [CBC]), serum chemistry; physical examination; vital signs; Eastern Cooperative Oncology Group (ECOG) performance status; and 12-lead electrocardiogram (ECG).

Safety analyses in general will be presented in tabular format with the appropriate summary statistics. Tabulations will be provided by dose cohort for the escalation part and the expansion part, by tumor type, and in total.

All safety analyses will be performed based on Safety Evaluable Set.

### 8.7.1 Dose Limiting Toxicities (DLT)

The number of DLTs identified among the DLT Evaluable Set will be listed and summarized for each dose cohort by the DLT criteria, and by the worst CTCAE grade v5.0, system organ class (SOC), and preferred term (PT).

### 8.7.2 Adverse Events (AE)

An AE is any untoward medical event that occurs to a subject following the start of study drug administration, whether or not the event is considered drug-related. Pre-existing conditions are not considered an AE unless the condition worsens by at least one grade following the start of study drug administration. Adverse events will be captured from the first dose of study drug and continue until 30 days after the last dose, or until a subsequent anti-cancer therapy is initiated if this occurs earlier than 30 days after the last study drug dose.

Treatment-emergent adverse events (TEAEs) are defined identically as AEs in this study.

An SAE is an AE that results in any of the following outcomes:

- Death
- A life-threatening condition
- An inpatient hospitalization or prolongation of an existing hospitalization
- A persistent or significant disability/incapacity
- A congenital anomaly/birth defect
- Important medical events that may not be immediately life-threatening or result in death or hospitalization but may jeopardize the patient or may require intervention to prevent one of the other outcomes listed above

Elective hospitalizations not in response to an AE is not considered an SAE. Adverse events constituting an SAE will be reported beginning from the first dose of study drug.

All deaths within 30 days of the last dose of study drug that are an outcome of an AE should be reported. Deaths due to disease progression should be reported as such and not as SAEs..

An overview of AEs will be provided by dose cohort, disease group and in total, summarizing subject incidence of the following information:

- Any TEAEs
- Drug-related TEAEs
- CTCAE grade  $\geq 3$  TEAEs
- Drug-related CTCAE grade  $\geq 3$  TEAEs
- Deaths due to AEs
- Treatment-emergent SAEs
- Drug-related treatment-emergent SAEs

- Dose interruption due to TEAEs
- Dose interruption due to drug-related TEAEs
- Dose reduction due to TEAEs
- Dose reduction due to drug-related TEAEs
- Discontinuation of study drug due to TEAEs
- Discontinuation of study drug due to drug-related TEAEs

The number and percentage of subjects with TEAEs and Grade 3/4/5 TEAEs will be summarized for each dose cohort, tumor type, and in total by SOC and PT. For these summaries, subjects with multiple adverse events will be counted only once per SOC and PT.

Additionally, the number and percentage of subjects with TEAEs will also be summarized by PT for each dose cohort, tumor type, and in total. Drug-related TEAEs, treatment-emergent SAEs, drug-related treatment-emergent SAEs, TEAEs leading to discontinuation of study drug, drug-related TEAEs leading to discontinuation of study drug, TEAEs leading to dose reduction/interruption of study drug, and drug-related TEAEs leading to dose reduction/interruption of study drug will be summarized in the same manner. For these summaries, subjects with multiple adverse events will be counted only once per PT.

Summaries will be provided by the worst CTCAE grade and PT for the number and percentage of subjects with TEAEs and drug-related TEAEs. Subjects with multiple adverse events will be counted only once by the highest CTCAE grade within a PT.

Furthermore, Tumor Lysis Syndrome (TLS) is considered AEs of special interest. The frequency and percentage of laboratory and clinical TLS (determined by Modified Cairo-Bishop criteria described in Appendix 10 of the protocol) will be tabulated by dose cohort, tumor type, and in total.

Listings will be provided for DLTs, SAEs, grade 3/4/5 AEs, AEs leading to dose reduction, AEs leading to dose interruption, AEs leading to discontinuation, and AEs leading to death. Additional listings may be provided for selected AEs of special interest. Moreover, a by-subject AE data listing including, but not limited to, verbatim, PT, SOC, CTCAE grade, action taken with voruciclib, and relationship to voruciclib will be provided.

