6.4. Serious Adverse Event (SAE) Reporting

Serious adverse events will be captured from the first dose of voruciclib monotherapy or venetoclax in the combination regimen and continue to be captured until 30 days after the last dose of study drug(s), or until a subsequent anti-cancer therapy is initiated. SAEs occurring after 30 days will be captured if believed to be related to study drug.

All SAEs, regardless of drug attribution, must be reported to the Sponsor or designee within 24 hours of the Investigator becoming aware of the SAE. The SAEs must be reported in EDC; however, if EDC is not accessible, a paper SAE form must be submitted to the Medpace Safety email or fax number within 24 hours of being aware of the event. When the EDC system becomes available, all applicable SAE information must be entered in EDC. The designee, as listed below, will also be specified in the Study Manual.

To report an SAE, contact Medpace Clinical Safety as listed below:

Email: [contact]

[contact], Option 3 OR [contact], Option 3

[contact] OR [contact]

Sites must follow-up to confirm receipt of the SAE Report.

The Investigator must report new significant follow-up information for these events to the sponsor or designee immediately (i.e., no more than 24 hours after becoming aware of the information). New significant information includes the following:

- New signs or symptoms or a change in the diagnosis
- Significant new diagnostic test results
- Change in causality based on new information

- Change in the event's outcome, including recovery
- Additional narrative information on the clinical course of the event

SAEs must be reported by each site to the appropriate Institutional Review Board (IRB)/Independent Ethics Committee (IEC) in accordance with local reporting requirements.

Reporting requirements will also be based on the Investigator's assessment of causality and seriousness, with allowance for upgrading by the sponsor as needed.

Deaths within 30 days of the administration of voruciclib or the administration of combination therapy must be reported as an SAE unless the death is due to disease progression. Deaths occurring >30 days after the last dose of voruciclib or the last dose of combination therapy must be reported as an SAE if considered by the investigator as related to study drug(s).

The Investigator should make every effort to obtain and send death certificates and autopsy reports for all deaths to the sponsor.

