9.5. Adverse Events

Adverse events will be collected at each visit as described in [Section 6](#).

A treatment-emergent AE (TEAE) is defined as an adverse event starting or worsening in CTCAE grade after the first dose until 30 days after the last dose of study drug(s), or start of new anti-cancer therapy, whichever is earlier. An adverse event reported ≥ 30 days after the last dose of study drug(s) will be reported and counted as TEAE if considered related to study drug and resulted in study drug discontinuation or an SAE.

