## 10. CHANGES FROM THE PROTOCOL SPECIFIED ANALYSES

No changes have been issued or planned.

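### The SAP's TEAE definition leaves out the protocol's clause for late drug-related events, so the TEAE tables would omit any related SAE reported 30 or more days after the last dose

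*SAP*

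**What the plan says.** **Protocol.** Section 9.5 defines a TEAE in two parts. The base part covers events that start or worsen after the first dose, up to 30 days after the last dose or the start of new anti-cancer therapy, whichever comes first. The second part covers AEs reported at or beyond 30 days after the last dose. Such an event "will be reported and counted as TEAE if considered related to study drug and resulted in study drug discontinuation or an SAE". Section 6.4 provides for collection of the serious ones: "SAEs occurring after 30 days will be captured if believed to be related to study drug". It also requires a death more than 30 days after the last dose to be reported as an SAE if the investigator considers it related.

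**SAP.** Section 8.7.2 states a single window: "Adverse events will be captured from the first dose of study drug and continue until 30 days after the last dose", or until new anti-cancer therapy if that is sooner. It then says: "Treatment-emergent adverse events (TEAEs) are defined identically as AEs in this study". On deaths it says: "All deaths within 30 days of the last dose of study drug that are an outcome of an AE should be reported". There is no counterpart to the second part of protocol 9.5 anywhere in the SAP. On departures from the protocol, SAP 10 says: "No changes have been issued or planned".

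**The concern.** The incidence of AEs, including DLTs, is the primary endpoint (protocol 10.2), and protocol 10.4.1 tabulates it as TEAEs by cohort. The SAP's overview and nearly all its AE tables are also built on TEAEs: any, drug related, Grade 3 or higher, serious, drug-related serious, and leading to discontinuation, reduction or interruption. What counts as a TEAE therefore decides what the main safety tables show.

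The events in the missing clause are the ones the protocol chose to keep despite their late timing, because they are attributed to study drug and are serious or led to stopping treatment. If the SAP is programmed as written, a late related SAE could sit in the database and in the SAE listing yet be absent from the treatment-emergent SAE table, with nothing in the SAP to explain the difference.

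**Working it through.** No figure in either document depends on the TEAE window, so there is none to reproduce. The check is a comparison of the two texts, followed by the arithmetic for one event.

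**1. The rules side by side**

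| Item | Protocol | SAP |
|---|---|---|
| Base window | To 30 days after last dose, or new anti-cancer therapy if earlier (9.5) | Same (8.7.2) |
| Late related SAE, 30 or more days after last dose | Counted as a TEAE (9.5); collected (6.4) | No rule; outside the only stated window |
| Late related non-serious AE leading to discontinuation | Counted as a TEAE (9.5); no explicit collection route | No rule |
| Related death after 30 days | Reported as an SAE (6.4) | Only a 30-day sentence (8.7.2) |
| Declared departure | Not applicable | None (10) |

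The base windows agree, including the new-therapy cutoff. The whole difference lies in the late clause and the related death rule.

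**2. Effect of one omitted event**

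Inputs: cohorts of 3 or 6 under the 3 + 3 rules (protocol 4.3); up to 12 subjects per expansion cohort (protocol 4.5); about 108 subjects in total (protocol 10.1). The documents give no rate of late related SAEs, so the calculation is per affected subject.

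If a late event is a subject's only qualifying event in a given row, that row falls by 1/n:

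- n = 3: 1/3 = 33.3 percentage points
- n = 6: 1/6 = 16.7 points
- n = 12: 1/12 = 8.3 points
- n = 108: 1/108 = 0.9 points

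If the subject already has another qualifying event in that row, the change is zero. The row for any TEAE is thus the least likely to move, and the row for drug-related treatment-emergent SAEs the most exposed. The actual n can differ a little, because safety tables use all treated subjects, including those replaced for DLT assessment (SAP 3.1.4 and 6.1).

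**3. What is not affected**

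DLTs are confined to Cycle 1 (protocol 4.4), so the 3 + 3 escalation counts do not depend on this definition.

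**The case against.** **The SAP may not exclude these events.** Its opening AE definition is open-ended: anything untoward after study drug starts. The 30-day sentence can be read as a collection rule rather than a table filter. SAP 7.5 adds that safety data collected after treatment discontinuation will be reported, with AEs followed according to protocol Section 6, which includes 6.4. On that reading every recorded AE is a TEAE, late related SAEs included. This stands as an ambiguity, but no more. The 30-day sentence is the only window the SAP gives and directly precedes the sentence equating TEAEs with AEs. SAP 7.5 covers reporting and follow-up, refers to Section 6 rather than 9.5, and does not make anything a TEAE. A primary-endpoint table should not depend on which reading the programmer chooses.

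**Version lag.** SAP 1 lists protocol versions only up to Amendment 11, while the current protocol includes Amendment 12. The documents do not show when the late clause entered, so the no-changes statement may have been accurate for its stated basis. That might explain the gap, but the current texts still conflict.

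**The protocol is not consistent either.** The AE recording footnotes in Appendices 1 to 3 stop at 30 days or new therapy, with no exception for late events, and the SAP sentence resembles them. This is correct, and it means the repair cannot be confined to the SAP.

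**Limited consequence.** The SAP calls the study exploratory (7.9). It lists SAEs, Grade 3 to 5 AEs and AEs leading to death separately, and its overview row for deaths due to AEs is not labelled treatment-emergent. These points reduce the harm, since a late event would probably be visible in a listing. They do not put it in the incidence tables.

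**Conclusion.** The point holds as an undeclared difference in a definition that feeds the primary-endpoint tables. On the natural reading of SAP 8.7.2, late related SAEs would be left out of the TEAE, treatment-emergent SAE and drug-related treatment-emergent SAE tables, contrary to protocol 9.5. The size is zero if no such event occurs. Otherwise it is 1/n for each subject who has no other qualifying event in the row. It is worth correcting because cohorts are small and the correction is simple.

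Three stronger readings are tempting but unsupported:

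- A reader might infer that known drug-related events are already missing from the tables. No late event is documented.
- A reader might infer that the SAP window closes earlier than the protocol's when new AML therapy starts soon after treatment. Protocol 9.5 has the same cutoff, and the documents say nothing on how soon new therapy starts.
- A reader might infer that dose escalation is compromised. DLTs are limited to Cycle 1 and are unaffected.

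The conclusion assumes that the 30-day sentence is applied as the table window and that late related SAEs reach the database as protocol 6.4 requires.

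**What to change.** 1. Replace the TEAE sentence in SAP 8.7.2 with both parts of the protocol 9.5 definition exactly as written. The late clause should apply to events reported 30 or more days after the last dose. Do not add a rule for events after new therapy but before day 30: protocol 9.5 has none, and adding one would create a new mismatch.
2. Add a late-onset flag, so that tables can be shown with and without these events.
3. Align the SAP's 30-day death sentence with protocol 6.4, so that related deaths after 30 days are covered.
4. If the sponsor prefers the narrower definition, declare and justify it in SAP 10.
5. In the protocol, settle the overlap at day 30 within 9.5, where both parts include that day, and reconcile the AE recording footnotes in Appendices 1 to 3 with 9.5.

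In the SAP, the cost is one definition, one death sentence and one programming flag. No new collection is needed for related SAEs. Late related non-serious events that led to discontinuation can be counted only if they are recorded, and the protocol does not assure that. Reported incidence may be slightly higher.

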### **8.7.3 Clinical Laboratory Tests**

Descriptive statistics will be provided for selected clinical laboratory test results (hematology, chemistry) and changes from baseline for each scheduled measurement day, the minimum or maximum post-baseline value as appropriate. Both scheduled and unscheduled post-baseline values will be included for the derivation of minimum/maximum post-baseline values.

Where criteria are available, laboratory values will be assigned toxicity grades, using NCI CTCAE v5.0. Directional shifts in laboratory toxicity grades (comparing baseline grade with worst post-baseline grade) will be analyzed using standard shift tables, presenting number and proportion of subjects and their maximum grade shift. For analyses without a toxicity grading scale, the shift table will present directional shifts from baseline to above or below the

laboratory standard normal range using the maximum increase and/or decrease observed throughout the course of treatment/observation. Both scheduled and unscheduled post-baseline values will be considered for maximum increase and/or decrease observed.

In addition, the number and percentage of subjects with treatment-emergent laboratory abnormalities (any grade and grade  $\geq 3$ ) will be presented for hematology and chemistry laboratory parameters if applicable. Treatment-emergent laboratory abnormalities are defined as post baseline laboratory abnormalities with worsening CTCAE grade from baseline. Post-baseline laboratory abnormality with unknown baseline grade will be considered as treatment-emergent.

All clinical laboratory data will be listed by subject using the International System of units (SI units). Values outside the normal ranges will be flagged.

#### **8.7.4 Vital Signs**

Descriptive statistics will be provided for the vital signs measurements (systolic blood pressure, diastolic blood pressure, heart rate, body temperature, and body weight) and changes from baseline for each scheduled measurement day, the minimum post-baseline value, and the maximum post-baseline value. Both scheduled and unscheduled post-baseline values will be considered for the derivation of minimum/maximum post-baseline value.

For systolic blood pressure and diastolic blood pressure, the clinical findings (normal, abnormal but not clinically significant, abnormal and clinically significant) will be tabulated for each scheduled measurement day and for the worst post-baseline assessment, by dose cohort and in total.

All vital sign measurements will be listed by subject.

#### **8.7.5 12-Lead Electrocardiogram (ECG)**

Electrocardiogram parameters (PR, RR, QRS, QT, and QTcF) will be summarized using descriptive statistics by dose cohort and in total. The arithmetic average of the 3 ECG interval durations from the triplicate will be calculated and treated as a single observation for the descriptive summaries.

Descriptive statistics will be provided for actual values (averages of triplicate) and for change from baseline for each scheduled measurement day, the minimum post-baseline value, and the maximum post-baseline value. Both scheduled and unscheduled post-baseline values will be considered for the derivations of minimum/maximum post-baseline values.

Frederica's correction to the reported QT interval, QTcF, will be derived (in milliseconds) for all subjects and time points as follows:

$$QTcF \text{ (msec)} = \frac{QT(\text{msec})}{\sqrt[3]{RR(\text{msec})/1000}}$$

All components for these calculations must be taken from the same assessment, which will be identified in the database by the date-time of the ECG recording.

The number and percentage of subjects with elevated QTcF over the post-baseline period will be presented for the following categories: QTcF worsening to >450 msec, >480 msec, and >500 msec from baseline, and increases in QTcF from baseline of >30 msec and >60 msec.

The overall interpretation of ECG assessments will be tabulated by dose cohort and in total at baseline and each evaluation time point. A shift table from baseline to the worst post-baseline assessment in terms of overall interpretation will also be provided for each dose cohort, disease group and in total. Both scheduled and unscheduled assessments will be considered for deriving the worst post-baseline evaluation.

All ECG measurements and overall interpretation will be listed by subject.

#### **8.7.6 Physical Examination**

Physical examination results will be listed by subject.

#### **8.7.7 ECOG Performance Status**

The ECOG performance status result at each scheduled visit will be tabulated by cohort, tumor type and in total. In addition, the worst ECOG performance status during the post-baseline period will be tabulated by cohort. Both scheduled and unscheduled post-baseline assessments will be considered when deriving the worst post-baseline ECOG performance status.

All ECOG performance status data will be listed by subject.

### **8.8 Analyses of Pharmacokinetics and Pharmacodynamics**

Analyses of pharmacokinetics and pharmacodynamics data will be conducted separately. The respective analysis plans will be specified in separate documents.

## **9. ADDITIONAL ANALYSES ON THE IMPACT OF COVID-19**

### **9.1 General Consideration**

COVID-19 pandemic may impact the conduct of the study from different aspects including quarantines, site closures, travel limitations, interruptions to the supply chain for the investigational product, or other considerations if site personnel or trial subjects become infected with COVID-19.

Start date and end date of COVID-19 impact will be determined to assess the impact of the COVID-19 pandemic to the study. COVID-19 impact date is defined as the date at which the site and/or overall study was impacted by COVID-19, resulting in changes to how assessments were conducted at the site and/or for the study overall.

## 9.2 Subject Disposition

Subject disposition will be summarized for each dose cohort and in total for all enrolled subjects. In addition, subject disposition will be tabulated by tumor type and in total. The following categories of subject disposition will be included:

- Subjects who were screened
- Subjects who were screen failures
  - Subjects who were screen failures due to COVID-19
- Subjects who were enrolled
- Subjects who were treated
- Subjects who discontinued from the study
  - Subjects who discontinued from the study due to COVID-19
- Subjects who completed the study and were still alive at EOS visit

For subjects who discontinued from the study, the primary reason for ending the study will be summarized. Specifically, discontinued early from the study due to COVID-19 impact will be summarized. Additionally, on-study deaths (defined as deaths during treatment period or within 30 days of treatment discontinuation) will be presented. The number and percentage of subjects in each defined analysis population will be tabulated as well.

All deaths that occur on study will be reported in a subject listing, which will include the primary cause of death and the number of days between the date of the first (and last) dose of study drug and death.

All subject disposition data will be presented in a data listing.

## 9.3 Protocol Deviations

Subjects with CSR-reportable protocol deviations by deviation category will be summarized for tumor type, therapy regimen and in total for all enrolled subjects. Specifically, protocol deviations related to COVID-19 will be categorized and summarized separately.

CSR-reportable protocol deviations and COVID-19 related non-reportable protocol deviations will be presented in a data listing.

